5.4.2 Protocol defined clinical schedule

5.4.2.1 Baseline Assessments

Assessment of visual function and retinal imaging of both eyes will be performed preoperatively as outlined in Section 5.6 (Table 2, Trial Assessments). For assessments requiring multiple baselines, testing is preferred on separate days within a maximum 3-month period to allow for day to day variation and test retest variability for individual participants. However, it is acknowledged that a balance will be achieved between what is pragmatic and appropriate for the different tests on an individual basis. Each set of baseline measurements may take up to 3 days to perform in total. In some instances, results for protocol specified baseline tests may be available through a subject's prior participation on the MGT005 LCA natural history study. As such, if the subject provides informed consent to use the results from the previously conducted tests, then these assessments will not need to be repeated at baseline.

Visual assessments results will be sent for reading and analysis to independent reading centres within the UK and US. For both sites Imaging for OCT and Fundus photography will be reviewed by the site teams but also sent for independent analysis by the Reading Centre, Queens University, Belfast during the course of the trial. Adaptive optics images will be sent to the Medical College of Wisconsin for reading and Octopus perimetry and Microperimetry will be sent to the Oregon Health and Science University Casey Eye Institute reading centre. All images will be saved under pseudo anonymised patient identifiers and images will only be taken of the patient's eye to ensure that patients will remain unidentified.

Up to 10 mL of blood will be sampled in order to assess baseline levels of T-cell responses to AAV5 and of circulating antibodies against AAV serotype 5 and *RPE65* so that immunological responses to vector capsids and transgene product might be determined following vector administration (collectively described as serology in Table 2, Trial A assessments). We anticipate that the majority of participants will have no detectable pre-existing circulating antibodies against AAV5 or *RPE65*. The presence or absence of circulating antibodies will not affect recruitment of the participant. All serology tests will be carried out at the sponsor's approved Laboratory in the UK.

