Colour vision testing will be undertaken using plate tests and computerised tests probing colour discrimination.

Retinal sensitivity will be determined using Octopus 900 full-field static perimetry and/or full field stimulus testing (FST) where available, and microperimetry (mesopic and scotopic). Where available, FST may be performed for enrolled paediatric patients at participating sites. The retinal locus of fixation will also be accurately determined using microperimetry.

Vision-guided mobility will be assessed by measuring the ability of each participant to navigate a simple route in a range of controlled illuminances.

Full-field electroretinography (ERG), pattern ERG (PERG) and multifocal ERG (mfERG) will be performed according to the International Society for Clinical Electrophysiology of Vision (ISCEV) standards to assess both generalised retinal (RPE, rod and cone systems) and isolated macular function. Modified ISCEV protocols may be necessary in young children using internationally recognised modified protocols. For young children, this procedure may be performed under general anaesthesia. ERG data will be analysed and interpreted by dedicated full-time Clinical Visual Electrophysiology Consultants with extensive experience and who are directly involved in determining ISCEV standards.

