The degree of intraocular inflammation will be assessed by slit-lamp biomicroscopy at each time point. A temporary intraocular inflammatory response is predictable following vitrectomy surgery. This is typically evident clinically on slit lamp biomicroscopy as 'flare' and cells in the anterior chamber and can be of moderate (2+) intensity. The degree of intraocular inflammation is expected to decline during the course of the first 8 weeks following the surgical procedure at which time the routine topical and systemic immunosuppression will be discontinued. Prolonged or recurrent intraocular inflammation will be managed conventionally by further topical and/or systemic immunosuppression.

(ii) Evaluation of immune responses

Up to 10mL of blood will be sampled to measure immune response. Blood serum will be isolated and analysed. Residual samples will be stored in an approved laboratory designated by the sponsor for use in future ethically approved research, with the participant's consent. Immunological assays will be performed as outlined in Section 5.6 (Trial Assessments) to investigate antibody responses to AAV capsid proteins and to RPE65 protein. Investigators performing these analyses will be masked to participant's identity.

(iii) Evaluation of biodistribution

Systemic biodistribution of vector genomes will be assessed as outlined in Section 5.6 (Trial Assessments) by PCR analysis of tears from the study eye (a compressed cellulose sponge placed under the eye lid until swollen), saliva (a minimum of 100 µL) and serum (100 µL). This test will be carried out in the institutional laboratory in the UK.

(iv) Assessment of visual function and retinal imaging

Assessment of visual function and retinal imaging will be performed as outlined in Section 5.6 (Trial Assessments) at baseline and at intervals following intervention. These assessments will be scheduled over a period of a day for visits at day 1, day 3, week 1, week 2, week 4 and week 6 after surgery, and up to 4 days for baseline examinations, and 3 months and 6 months following intervention. For day 1 and 3 refraction cannot reliably be measured. Therefore, the most recent refraction measurement will be used.

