5.10.4 Statistical Methods

5.10.4.1 Statistical Analysis Plan

A formal statistical analysis plan will be written by the trial sponsor and approved by the IDMC. This trial is an open label, no crossover, Phase I/II trial involving a small number of participants, and analysis of the primary and secondary outcomes will be descriptive in nature.

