5.10.4.3 Statistical Methods - Secondary Outcome Analysis

The secondary outcomes are measures of the efficacy of the ATIMP; these will be performed on an individual participant basis and will be primarily descriptive in nature. Standard assessments will be used to measure visual function and established methods of analysis, appropriate for the assessment will be used to evaluate the data. For specialist assessments, data will be analysed by the expert team member(s) who developed the assessment. Final data will be reported descriptively.

Efficacy will be indicated by:

- 1) Any improvement in visual function from baseline that is greater than the test-retest variation for that test and is sustained for at least two consecutive assessments.
- 2) Any improvement in retinal function from pre-intervention assessment that is greater than the test-retest variation and measurable by electroretinography (ERG)

If no ERG was previously detectable, then the presence of any reproducible response with appropriate waveform would be clinically significant. If an ERG was there to start with, any of the following would be significant:

- an improvement in amplitude of >50 % in DA 0.01 b-wave (rod system sensitivity);
- bright flash DA 10 a- wave (photoreceptor improvement);
- the 30Hz flicker; and
- the LA 3.0 photopic a- and b-waves.

In terms of timing: > 3ms improvement in photopic parameters and bright flash DA 10 a-wave; 6ms for the DA 0.01 and DA 10.0 b-waves.

Measures will be reported individually and aggregated across participants as the proportion who satisfy the above criteria.

Quality of life patient reported outcome measures will be used to correlate a participant's feeling about their own wellbeing with clinical observations.

Any deviations from the original statistical plan will be approved by the CMT and IDMC and described in the final report, as appropriate.

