6.7 Declaration of Interests

The trial is funded by MeiraGTx UK II Ltd.

[name] declares a financial interest in the company and receipt of payment for consultancy services.

[name] declares a financial interest in the company and receipt of payment for consultancy services.

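### No masking of efficacy readers to treated eye or visit is stated, although stored outputs such as ERG traces could be read under codes at little cost

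*Combined protocol and SAP*

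**What the plan says.** The design is open: "This trial is an open label, no crossover, Phase I/II trial involving a small number of participants" (5.10.4.1). Three places deal with who reads the efficacy tests.

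- **5.10.4.3**: for specialist assessments, "data will be analysed by the expert team member(s) who developed the assessment". The term is not defined and no masking is mentioned.
- **5.4.2.1, reading centres**: "Visual assessments results will be sent for reading and analysis to independent reading centres within the UK and US". OCT and fundus photographs are "reviewed by the site teams but also sent for independent analysis by the Reading Centre". Outside centres are also named for adaptive optics images and for Octopus perimetry and microperimetry. Images are stored under pseudonymised patient identifiers.
- **5.4.2.1, electrophysiology**: "ERG data will be analysed and interpreted by dedicated full-time Clinical Visual Electrophysiology Consultants". Their experience is described; neither independence nor masking is.

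The only masking statement concerns the immune-response assays in 5.4.2.3: "Investigators performing these analyses will be masked to participant's identity".

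Section 4.1.6 says the untreated fellow eye may act as a control. Section 5.10.4.3 reports efficacy for each participant and as the proportion meeting the criteria.

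**The concern.** With no randomised arm, evidence of efficacy comes from comparing each participant with baseline and, if it is used, the treated eye with the fellow eye. Both comparisons depend on readings made in the same way before and after treatment and in both eyes. A reader who knows the eye and the visit may, without intending to, read an equivocal trace more generously when it comes from the treated eye after surgery. Such an error always goes in the direction of benefit and cannot be removed at analysis.

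At stake is the credibility of the responder proportion. Section 5.11.2 sends key efficacy outcomes to the IDMC, and 6.13.1 allows findings to be published while the trial is running.

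**Working it through.** The documents give no figure on this point, so there is none to reproduce. The check sets the passages side by side.

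**Step 1. Who reads what, and what is hidden from them**

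| Output | Reader named | Independence stated | Hidden from reader |
|---|---|---|---|
| OCT, fundus photographs | Site teams, plus a reading centre (5.4.2.1) | Yes, for the centre | Patient identity only (pseudonymised) |
| Adaptive optics images | Outside centre (5.4.2.1) | Yes | Patient identity only (pseudonymised) |
| Octopus perimetry, microperimetry | Outside reading centre (5.4.2.1) | Yes | Nothing on eye or visit |
| ERG, PERG, mfERG | Electrophysiology consultants (5.4.2.1) | Not stated | Not stated |
| Vision-guided mobility, colour vision | None named | Not stated | Not stated |
| Specialist assessments (undefined) | Developers of the test (5.10.4.3) | No | Not stated |
| Immune assays (not efficacy) | Laboratory investigators (5.4.2.3) | Not stated | Participant identity |

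No row hides treated eye or visit. For imaging and perimetry the gap is masking alone. For ERG and mobility, neither independence nor masking is stated.

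**Step 2. Where judgement enters**

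Section 5.10.4.3 has two function criteria. The first (visual function) requires a gain beyond test-retest variation at two consecutive assessments. The second (ERG) has no such confirmation rule. It splits by baseline:

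- ERG present at baseline: numeric limits apply, such as an amplitude gain above 50% or a timing gain above 3 ms.
- ERG not detectable at baseline: any repeatable signal with a suitable waveform counts. The reader decides.

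**Step 3. Why the missing confirmation rule matters (illustration only)**

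Assumptions, none from the documents: one measure, an eye with no true change, normal errors with within-subject SD 1, one baseline reading, a threshold of 1.96 × √2 = 2.77 SD, and a reader who shifts post-treatment readings by b SD.

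- One later reading: P = 1 − Φ((2.77 − b)/√2) = 1 − Φ(1.96 − b/√2).
- Two later readings, both above threshold: P = ∫ [1 − Φ(2.77 + e − b)]² φ(e) de, where e is the baseline error.

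| b | One reading | Both of two readings |
|---|---|---|
| 0 | 1 − Φ(1.96) = 2.5% | 0.46% |
| 0.5 | 1 − Φ(1.61) = 5.4% | 1.4% |
| 1 | 1 − Φ(1.25) = 10.5% | 3.5% |
| 1.5 | 1 − Φ(0.90) = 18.4% | 7.7% |

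If the baseline is the mean of three readings, or the threshold is 1.96 × √(1 + 1/3) = 2.26 SD, the two-reading figures change. Across these variants they run from 0.9% to 3.5% at b = 1 and from 3.2% to 9.2% at b = 1.5.

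Confirmation at two visits gives some protection against reader shift, and the ERG criterion lacks it. The model does not describe the waveform-judgement branch, and nothing in the documents fixes b.

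**The case against.** **Silence is not absence.** Section 5.4.2.1 refers to a study manual for further test details, and 5.10.4.1 announces a formal SAP still to be written. Neither is among the documents. This stands: the claim can only be that no masking is stated.

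**Independent reading is already planned.** The opening sentence on reading centres is general and could be meant to cover more than the tests then listed. This stands in part. Independence and pseudonymised identifiers are real safeguards, but neither hides eye or visit. The general sentence also conflicts with giving specialist tests to their developers and ERG to consultants.

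**ERG is not a home-made test.** It follows ISCEV standards, and its criteria are numeric where a baseline response exists. This stands. A reader might infer that ERG is analysed by those who invented it; nothing in the documents says so. Developer-led analysis and unmasked ERG reading are separate issues, and the judgement concern is confined to the branch with no detectable baseline response.

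**The immunology masking is a weak precedent.** It hides identity only, much like the image identifiers. This stands.

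**Masking is not always possible.** Mobility is live navigation, and colour vision is tested in person. Coding files cannot mask participant or tester, and surgical change may reveal the treated eye on an image. This stands and limits the remedy.

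A reader might also infer three things that the documents do not support:

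- that the financial interests declared in 6.7 belong to the efficacy readers; no link is given;
- that both eyes have ERG at every visit; 5.4.2.1 specifies both eyes preoperatively, and the available text of Table 2 has no ERG row;
- that a count of false responders can be obtained by applying an assumed error rate to all 27 participants; the rate has no source, and the multiplication assumes that nobody truly responds.

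**Conclusion.** The point holds as a cheap improvement. The documents state no masking of efficacy readers or analysts to treated eye or visit, do not define the specialist assessments given to their developers, and leave 5.4.2.1 and 5.10.4.3 unreconciled on who reads what. Exposure is greatest for ERG without a detectable baseline response, where a single judged reading can make a responder.

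The size of any bias cannot be derived from the documents; the illustration rests wholly on an assumed reader shift. The primary safety outcome is not touched, and the efficacy analysis is descriptive. The fellow eye is only a possible control, and 5.10.4.3 specifies no comparison with it, so unmasked reading weakens that use of the fellow eye but does not abolish it. The conclusion would change if the study manual or the formal SAP already specifies masked reading.

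**What to change.** In 5.10.4.3 and 5.4.2.1, carried into the formal SAP:

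1. Define the specialist assessments and reconcile the two sections, naming the reader for each efficacy test.
2. Have the existing readers score stored outputs under random codes that hide eye and visit: ERG traces, perimetry and microperimetry outputs, retinal images, and mobility recordings if any are made. Keep repeat traces from one eye and session together, so that repeatability can still be judged.
3. Release the codes only after scores are locked, then derive change from baseline and responder status from the locked scores.
4. State that masking is not possible for live, effort-dependent testing and is incomplete where images show surgical change.

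The cost is a small coding and file-handling step with the same readers. No extra tests or participants are needed, and site teams can keep their own review of the images. The remaining weakness is incomplete masking for some images and none for live tests, which the report should acknowledge.

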4.1.6 Explanation for Choice of Comparators

There is no currently approved treatment for retinal dystrophy caused by mutations in *RPE65*, thus there are no comparators in this study. The contralateral fellow eye will be left untreated to minimize the risk to visual function and may also serve as a control.

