There is wide variability in the ability of children of different ages to undertake some of the proposed tests; the evaluations for children will be restricted to those tests that they are able to perform reliably.

Tests that will be performed in all participants are:

MGT003, Gene Therapy Trial for LCA OPTIRPE65

1. Serological tests
2. Blood pressure
3. Haematology
4. Biochemistry
5. Ocular examination
6. Intraocular pressure
7. Colour fundus photography
8. Spectral Domain Optical coherence tomography (SD-OCT)
9. Fundus Autofluorescence imaging (FAF)
10. Best corrected visual acuity
11. Full-field electroretinography (ERG)
12. Pattern electroretinography (PERG)

Tests that will be performed where possible are:

13. Contrast sensitivity
14. Reading assessment
15. Colour vision testing
16. Microperimetry (mesopic and scotopic)
17. Octopus900 full-field static perimetry
18. Vision-guided mobility
19. Multifocal electroretinography (mfERG)
20. Adaptive optics (AO) imaging
21. QOL questionnaires

Further details of clinical assessments can be found in the OPTIRPE65 study manual.

(i) Ocular examination and retinal imaging

Ocular examination by slit lamp biomicroscopy will be used to assess the anatomical integrity of the eyes and quantify any intraocular inflammation. During the examination, intraocular pressure will be determined by tonometry.

Retinal imaging includes colour fundus photography (ETDRS 7 standard fields), FAF, SD-OCT, and AO imaging. FAF imaging allows visualisation of the retinal pigment epithelium (RPE) by taking advantage of its intrinsic fluorescence derived from its lipofuscin content. SD-OCT imaging enables measurement of retinal thickness and provides information about the integrity of the layers of the retina. AO imaging provides direct visualization of the photoreceptor and RPE mosaics *in vivo*.

(ii) Functional and Participant-Related Outcome assessments

Where possible the participant will complete an age-appropriate Impact of Visual Impairment (IVI) vision-specific quality of life questionnaire, and EQ5D-5L and EQ-5D-Y questionnaires.

MGT003, Gene Therapy Trial for LCA OPTIRPE65

Reading ability, including reading acuity, maximum reading rate, and critical print size will be assessed with MNRead and International Reading Speed Texts.

Best-corrected ETDRS visual acuity will be measured in each eye. Contrast sensitivity will be measured using the Pelli-Robson chart.

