5.5.2 Secondary Outcomes

The secondary outcomes are measures of the efficacy of the ATIMP; these will be performed on an individual participant basis and will be descriptive in nature. Secondary outcomes are:

- Any improvements in visual function from baseline that are greater than the test-retest variation and are sustained for at least two consecutive assessments.
- Any improvement in retinal function from pre-intervention that is greater than the test-retest variation and measurable by electroretinography (ERG).

If no ERG is previously detectable, then the presence of any reproducible response with appropriate waveform would be significant. If an ERG is there to start with, any of the following would be significant: an improvement in amplitude of >50 % in DA 0.01 b-wave (rod system sensitivity); bright flash DA 10 a-wave (photoreceptor improvement); the 30Hz flicker; and the LA 3.0 photopic a- and b-waves. In terms of timing: > 3ms improvement in photopic parameters and bright flash DA 10 a-wave; 3-6ms for the DA 0.01 and DA 10.0 b-waves.

- Quality of life will be measured by the Impact of Visual Impairment (IVI) questionnaire and the EQ5D- 5Land EQ-5D-Y

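### The efficacy criteria do not say which eye they apply to and make no use of the untreated fellow eye, so on effort-dependent tests a practice gain shared by both eyes can be counted as response

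*Combined protocol and SAP*

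**What the plan says.** Section 4.1.6 gives the lack of an approved treatment as its reason, "thus there are no comparators in this study", and then adds: "The contralateral fellow eye will be left untreated to minimize the risk to visual function and may also serve as a control". That is the only mention of a control role for the fellow eye.

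The first secondary outcome in section 5.5.2 is: "Any improvements in visual function from baseline that are greater than the test-retest variation and are sustained for at least two consecutive assessments". Section 5.10.4.3 repeats it as "Any improvement in visual function from baseline that is greater than the test-retest variation for that test", again with the two-assessment condition, and section 1.3 has the same rule. The second criterion concerns electroretinography (ERG) and carries its own amplitude and timing thresholds. Section 5.10.4.3 combines the results as follows: "Measures will be reported individually and aggregated across participants as the proportion who satisfy the above criteria". None of these sections names the eye, sets a treated-minus-fellow contrast or makes any allowance for learning.

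On data collection, section 5.4.2.1 says: "Assessment of visual function and retinal imaging of both eyes will be performed preoperatively". For acuity it says: "Best-corrected ETDRS visual acuity will be measured in each eye". Section 5.4.2.3, on assessments after surgery, does not say whether both eyes are tested. Table 2 in section 5.6 schedules perimetry, contrast, reading and colour tests at three baseline visits and again at weeks 12 and 24. Microperimetry has one further earlier visit, and acuity is measured at every follow-up visit.

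**The concern.** The secondary objective (section 4.2.2) is causal: does the vector improve sight? With no comparator arm, the untreated eye is the only concurrent reference. It belongs to the same participant, who follows the same visit schedule and takes the same systemic steroid course. Where it is tested, it also gets the same practice.

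Test-retest variation describes random scatter around a stable level. A participant who becomes better at perimetry or chart reading moves to a higher level and stays there. The two-assessment rule therefore offers little protection, because a learned gain is present at both visits. If fellow eyes met the criterion as often as treated eyes, the stated proportion would not show it. At stake is how the efficacy summary is read, and whether use of the control is fixed in advance or chosen after the data are seen.

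**Working it through.** **The plan's own figures.** The plan states no efficacy power, alpha or effect size, so there is none to reproduce. The head counts do reproduce: 3 doses × 6 = 18, 18 + 9 = 27 participants, and 6 + 9 = 15 at the maximum tolerated dose.

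**Inputs from the documents.** Up to three baselines; two follow-up assessments (weeks 12 and 24) for most effort-dependent tests; response requires both to exceed test-retest variation.

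**Assumptions (not in the documents).** Measurement error has within-person SD 1, independent between visits. Baseline is the mean of three visits. The threshold is the 95% test-retest limit, c = 1.96 × √2 = 2.77 SD. There is no treatment effect. A practice gain d, measured above the baseline mean, is present at both follow-up visits and equal in the two eyes.

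**One-eye rule.** Given baseline error b, each follow-up change exceeds c with probability 1 − Φ(c + b − d). Both must do so, hence

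P(d) = ∫ φ(b; 0, SD = 1/√3) × [1 − Φ(c + b − d)]² db.

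**Between-eye rule.** The same two-visit rule is applied to treated-minus-fellow change, with threshold c × √(2(1 − ρ)), where ρ is the between-eye error correlation. The gain d cancels. Simulation (1,000,000 draws) with ρ = 0 and ρ = 0.5 gave the same result for this rule.

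| Gain d (SD) | One-eye rule, per test | Expected false responders of 27 (27 × P) | Between-eye rule, per test |
|---|---|---|---|
| 0 | 0.03% | 0.01 | 0.03% |
| 1 | 0.9% | 0.24 | 0.03% |
| 1.5 | 3.2% | 0.86 | 0.03% |
| 2 | 9% | 2.4 | 0.03% |

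The integral and the simulation agree for the one-eye rule.

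**Sensitivity to the baseline.** Section 5.4.2.1 does not say how the baseline visits are combined. With a single baseline value (SD of b = 1), the one-eye rates at d = 0, 1 and 1.5 are 0.5%, 3.5% and 7.7%. Averaging three visits is the more natural reading of the schedule and is the case used above.

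**Reading the table.** The threshold and two-visit rule control random error well (0.03%). On a single test the practice problem is small up to about 1 SD and becomes material near 2 SD. The two-visit model does not fit acuity, which has many more follow-up visits.

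**The case against.** The strongest reply is that these are secondary, descriptive, individually reported outcomes in a phase I/II safety trial. No efficacy test or stated decision rule depends on the proportion. Section 5.10.4.1 promises a separate statistical analysis plan, which is not among the documents reviewed, and section 5.10.4.3 refers to established methods for each assessment. The plan also has real safeguards: repeat baselines, a test-retest threshold and a two-assessment rule. All of this stands, and it limits the weight of the point. It does not answer it, because the criteria are already written in the protocol and leave the control optional.

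A reader might infer more than the text supports:

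- **That the criteria use the treated eye alone.** They name no eye. The finding is an unspecified eye and an undefined contrast.
- **That ERG is equally exposed.** It is an objective recording, largely not open to practice. The point concerns effort-dependent tests under the first criterion.
- **That false response builds up across tests.** If any of six independent tests could qualify, the three-baseline rates would be 5% at 1 SD and 18% at 1.5 SD. The documents do not list six qualifying tests, and tests on one eye share participant, day and retina, so independence is not supported.
- **That the fellow eye removes all bias.** Participants know which eye was treated, so effort and expectation can favour it. Section 5.4.2.2 (Operative procedure) expects the poorer-seeing eye to be treated, so floor effects, regression to the mean and practice may differ between eyes.
- **That fellow-eye follow-up is already secured.** Testing of both eyes is explicit only before surgery. The per-eye statement covers acuity.

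**Conclusion.** The point holds as a cheap improvement. The efficacy criteria name no eye and leave the only concurrent comparator unused, so a lasting practice gain common to both eyes can pass the first criterion on effort-dependent tests done one eye at a time.

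The size is conditional. Under the stated model it is about 1 false response per 100 participants per test at a 1 SD gain, and about 9 per 100 at 2 SD. The assumed gain, the 95% threshold, averaging of three baselines and independent visit errors all drive these figures. Confidence is high that the contrast is undefined in the documents reviewed, and low about how large any practice gain would be.

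The documents do not support the conclusion that the trial would report efficacy wrongly. They show that the stated summary could not separate a vector effect from a shared gain. Neither the primary safety outcome nor dose escalation is affected.

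**What to change.** 1. In sections 5.5.2 and 5.10.4.3 (and the summary in 1.3), state that the criteria apply to the treated eye.
2. For each test done one eye at a time, apply the identical criteria to the fellow eye. Beside the treated-eye proportion, report whether the treated, fellow, both or neither eye met them. Add the treated-minus-fellow difference in change, with both eyes' baselines shown.
3. Interpret efficacy in light of this contrast. Do not exclude matched responses automatically, since that would discard a large treated-eye gain whenever the fellow eye just crosses the threshold.
4. In section 4.1.6, replace the optional wording with a statement that the fellow eye will serve as the within-participant control.
5. Confirm in sections 5.4.2.3 and 5.6 that one-eye tests after treatment cover both eyes.
6. Treat fellow-eye ERG as supportive only, as a check on session-to-session variation.

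The cost is wording and a few table columns, plus testing time if fellow-eye follow-up is not already intended. The efficacy figure may look less favourable. The eyes are not fully exchangeable, tests done with both eyes open gain nothing, and expectation effects specific to the treated eye remain.
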